6.7.4 RP2D

The RP2D may be equal to, but may not exceed, the MTD. A RP2D below the MTD may be considered given the overall tolerability of the treatment regimen including the frequency of AEs that are not DLTs and the frequency of dose modifications.

6.8 Required QT Monitoring and QT Interval Prolongation Instructions

- 6.8.1 Monitoring
 - A 12-lead ECG and evaluation of QTc interval will be performed weekly in cycle 1, on day 1 of cycle 2, and then on day 1 of every other cycle.
 - If the QTc is ≥ grade 2, follow instructions in Table 7 for additional observation and/or ECG requirements.
 - If medically indicated, ECGs may be performed any time during treatment and follow-up.
- 6.8.2 Requirements for Manual Read of QTc Interval

Any time QTc is evaluated:

- If the HR is < 60 bpm or >100 bpm, manual read of the QT interval by a cardiologist is required; also the Fridericia formula for QT interval correction should be used (ie, QTcF).
- If HR is between 60-100 bpm, a manual read of QTc is NOT required.

Any questions or concerns about ECG readings will be reviewed with a cardiologist.

6.8.3 Concurrent Use of Drugs Known to Cause Clinically Significant QT Prolongation

To the extent possible, concurrent use of study medications with drugs known to cause clinically significant QT prolongation should be avoided. Such drugs may be identified at the Credible Meds website (http://crediblemeds.org/login). The Credible Meds website requires free user registration to view the list of clinically relevant QT-prolonging drugs, eg, those known to carry a risk of causing Torsade de pointes. QT-prolonging drugs to be avoided during this trial are shown in the Credible Meds list of "drugs with known TdP risk."

When concurrent use of study treatment with any drug on the Credible Meds list of "drugs with known TdP risk" cannot be avoided, review QTc prior to concurrent use. If, **prior to concurrent use**, the QTc is:

- Grade 0 (< 450 ms), follow-up QTc evaluation should be performed at the next follow-up visit.
- Grade 1 (450-480 ms), follow-up QTc evaluation should be done within 8 days after concurrent use starts.
- Grade 2 (481-500 ms), hold study treatment until follow-up ECG at next possible opportunity shows QTc ≤ grade 1 (≤ 480 ms); evaluate QTc within 8 days after reintroduction of study treatment.
- 6.8.4 Any new onset of dysrhythmia on ECG during treatment will be reviewed and managed with input from cardiology.

6.8.5 Follow instructions in Table 7 for any episode of syncope (grade 3) or near-syncope (pre-syncope grade 2) or QTc grade 3 (≥ 501 ms on 2 or more ECGs), or grade 4 (≥ 501 ms or > 60 ms change from baseline and Torsade de pointes or polymorphic ventricular tachycardia or signs/symptoms of serious arrhythmia).

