7.5.2 Dose Modification Instructions for AR-42

In addition to the general dose modification instructions provided in Section 7.4, and the dose reduction steps listed on the table above, dose modification instructions for specific toxicities related to AR-42 are listed in Table 5.

Note: Some pazopanib-related toxicities may result in medical reasons to also hold, omit, or discontinue AR-42. When AR-42 modification/discontinuation is also required, the pazopanib dose modification tables (Table 7, Table 8, Table 9, and Table 10) will also specify the required AR-42 modification.

Grade (CTCAE v4.0)	AR-42 Modification (Refer to Table 4 for AR-42 dose reduction steps)
Blood and Lymphatic System Disorders	
Grade 3 or 4 anemia	Hold/omit ^A AR-42 until resolution to ≤ grade 2; transfusions are permitted.
Grade 3 or 4 febrile neutropenia	Hold/omit ^A until resolved; reduce dose by one dose reduction step when resuming treatment. ^B
Infections and Infestations	
Grade 3 infection	Hold/omit ^A until recovered to ≤ grade 2; at the investigator's discretion, the dose may be reduced by one dose reduction step when resuming treatment. ^B
Grade 4 infection	Hold/omit ^A until recovered to ≤ grade 2; reduce dose by one dose reduction step when resuming treatment. At the investigator's discretion, study treatment may be discontinued.
Investigations	
Grade 3 or 4 ECG QTc interval prolonged	Refer to Table 7 for instructions.
Grade 3 neutrophil count decreased; required ≤ 7 days for recovery to ≤ grade 2	Hold/omit ^A until ≤ grade 2. Dose reduction is not required when resuming treatment.
Grade 3 neutrophil count decreased; > 7 days required for recovery to \leq grade 2	Hold/omit ^A until ≤ grade 2; reduce dose by one dose reduction step when resuming treatment.
Grade 4 neutrophil count decreased	
Grade 3 platelet count decreased; ≤ 7 days required for recovery to ≤ grade 2	Hold/omit ^A until ≤ grade 2. Dose reduction is not required when resuming treatment.
Grade 3 platelet count decreased; > 7 days required for recovery to ≤ grade 2 Grade 4 platelet count decreased	Hold/omit [▲] until ≤ grade 2; reduce dose by one dose reduction step when resuming treatment.
Nervous System Disorders	
Grade 2 pre-syncope or grade 3 syncope (potentially reflecting cardiotoxicity)	Refer to Table 7 for instructions.
Other Toxicities Possibly Related to AR-42	(see footnote c)

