Grade 3 ECG QTc interval prolonged See Section 6.8 for additional instructions regarding QT monitoring.	 Hold/omit^A pazopanib and AR-42. Check potassium, magnesium, and calcium levels; immediately administer potassium, magnesium, and/or calcium to achieve potassium level of ≥ 4 mEq, magnesium level of ≥ 2 mEq, and calcium WNL. Consider chronic supplementation for maintenance of electrolytes. Review with investigator prior to patient's next scheduled treatment, considering the following: Hold pazopanib and AR-42 until QTc recovers to pre-study treatment baseline (≤ grade 1 [≤ 480ms]). When QTc returns to baseline, resume pazopanib and AR-42 with additional QTc monitoring at earliest opportunity within 8 days after resuming study treatment. If QTc prolongation is thought to be related to pazopanib, decrease pazopanib and AR-42 doses by one dose reduction step when resuming study treatment. For recurrent grade 3 QTc thought to be related to pazopanib and AR-42. 			
Grade 4 ECG QTc interval prolonged	Discontinue pazopanib (also discontinue AR-42).			
Elevation in AST, ALT, and/or bilirubin	Refer to Table 8 .			

Table 7.	Pazopanib	Dose	Modification	Instructions
	i uzopullio	0000	mounounon	in ou douono

 ≥ Grade 2 Reversible Posterior Leukoencephalopathy Syndrome (RPLS) Grade 2 pre-syncope or grade 3 syncope (potentially reflecting cardiotoxicity) 	 An evaluation for RPLS should be performed if the patient presents with seizures, headache (in conjunction with other RPLS symptoms), visual disturbances, confusion, or altered mental function. If RPLS is diagnosed, discontinue pazopanib (also discontinue AR-42). Hold/omit^A pazopanib and AR-42. Obtain 12-lead ECG for cardiology review/consultation. Check potassium, magnesium, and calcium levels; immediately administer potassium, magnesium, and/or calcium to achieve potassium level of ≥ 4 mEq, magnesium level of ≥ 2 mEq, and calcium WNL. If ECG shows new dysrhythmia or QTc ≥ grade 2 (> 480ms), hospitalize for monitoring with cardiology consultation. Hold pazopanib and AR-42 until any potassium, magnesium, and

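### A single asymptomatic on-treatment QTc of 501 ms or more triggers no mandatory prompt repeat ECG or hold, because the Section 6.8.1 pointer for grade 2 or higher finds no matching row in Table 7

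*Combined protocol and SAP*

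**What the plan says.** Section 6.8.1 schedules the ECG and QTc evaluation to be "performed weekly in cycle 1, on day 1 of cycle 2, and then on day 1 of every other cycle". Table 20, footnote J, puts the later ECGs at day 1 of cycles 4, 6 and so on, within a week either way. Section 6.8.1 also directs sites, for any QTc of grade 2 or higher, to Table 7 "for additional observation and/or ECG requirements".

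Three places then say what happens at each grade:

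- Section 6.8.5 refers to Table 7 for syncope, near-syncope, "QTc grade 3 (≥ 501 ms on 2 or more ECGs") and grade 4. Grade 4 also needs Torsade de pointes, polymorphic ventricular tachycardia or signs or symptoms of serious arrhythmia.
- Table 7 (Section 7.7) has a row for "Grade 3 ECG QTc interval prolonged", which holds both drugs and corrects electrolytes, and a row for grade 4, which discontinues both. Its one mention of grade 2 QTc is inside the pre-syncope/syncope row: "QTc ≥ grade 2 (> 480ms), hospitalize for monitoring with cardiology consultation".
- Table 5 (Section 7.5.2), for AR-42, refers only "Grade 3 or 4 ECG QTc interval prolonged" to Table 7.

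Section 6.8.3 covers a patient who cannot avoid a drug with known Torsade risk. If the QTc before that drug starts is in the next band down, the text is explicit: "Grade 2 (481-500 ms), hold study treatment until follow-up ECG at next possible opportunity shows QTc" has returned to grade 1 or lower.

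**The concern.** The pointer in Section 6.8.1 promises an instruction that Table 7 does not visibly contain for an asymptomatic patient. The gap matters most for a high single value. Grade 3 depends on a second ECG, and outside the regular schedule nothing requires that second ECG to be done. A site following the text exactly could record 501 ms or more once, see that it is not yet grade 3, and go on dosing both drugs until the next scheduled ECG.

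The protocol is more demanding at lower values elsewhere. Section 6.8.3 orders a hold and an early ECG at 481-500 ms in the concomitant-drug setting. At screening, Section 4.2.13 orders electrolyte checks and a repeat ECG for a QTc above 450 ms, and 501 ms is 501 - 450 = 51 ms above that limit. QT prolongation and Torsades de Pointes are among the pazopanib warnings listed in Section 9.2.10. What is at stake is patient safety and consistent handling across sites.

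**Working it through.** There is no plan figure to reproduce. The check follows one reading of 501 ms or more, without symptoms or dysrhythmia, through the text, and then computes the wait to the next required ECG.

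**Path of the reading**

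1. Section 6.8.3 gives grade 2 as 481-500 ms. The reading lies above that band.
2. Section 6.8.5 needs two or more ECGs for grade 3. There has been one.
3. Grade 4 needs an arrhythmia or its signs or symptoms. There are none.
4. If the reading is nevertheless treated as grade 2 or higher under Section 6.8.1, Table 7 offers only the grade 3 row, the grade 4 row and the syncope row. Read strictly, none applies.
5. Table 10 covers toxicities not addressed in the earlier tables. Even if it is taken to apply, its grade 2 row leaves interruption to the investigator and says nothing about ECGs.
6. Section 6.8.2 makes a manual read by a cardiologist compulsory only when the heart rate is below 60 or above 100 bpm.

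**Wait to the next required ECG, cycles not extended**

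Inputs: cycle 1 visits on days 8, 15 and 22, each within 24 hours (Table 19, footnote B); cycle 2 day 1 is study day 29, or up to 3 days earlier (Table 20, footnote A), so days 26-29; cycle 4 day 1 is day 1 + 3 x 28 = 85, within 7 days (footnote J), so days 78-92.

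| Reading at | Next required ECG | Shortest wait | Longest wait |
|---|---|---|---|
| Day 8 or 15 | Next weekly visit | 7 - 2 = 5 days | 7 + 2 = 9 days |
| Day 22 (21-23) | Cycle 2 day 1 (26-29) | 26 - 23 = 3 days | 29 - 21 = 8 days |
| Cycle 2 day 1 (26-29) | Cycle 4 day 1 (78-92) | 78 - 29 = 49 days | 92 - 26 = 66 days |

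Later gaps have the same nominal length, 2 x 28 = 56 days. With a one-week window at both ends they run from 56 - 14 = 42 to 56 + 14 = 70 days. Cycles extended to 5 weeks lengthen all of these.

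Between the cycle 2 and cycle 4 ECGs, the 9 AR-42 doses of cycle 2 and the 9 of cycle 3 are scheduled (2 x 9 = 18 at least), with pazopanib daily. This assumes that no dose is missed or held and that the cycle 2 day 1 ECG precedes that day's dose.

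**The case against.** The strongest reply is that a sensible investigator would not be stuck. The syncope row in Table 7 glosses grade 2 or higher as above 480 ms, so a reading of 501 ms does reach Table 7, and the grade 3 row there does not restate the two-ECG condition. Some sites would hold both drugs at once. Section 6.8.2 adds, in mandatory wording, "Any questions or concerns about ECG readings will be reviewed with a cardiologist", and Section 6.8.1 allows an ECG at any time if medically indicated. The 481-500 ms band is taken from a section on concomitant drugs. Between the cycle 2 and cycle 4 ECGs there are also visits with chemistry (cycle 2 day 15) and with examination, adverse event assessment and chemistry (cycle 3 day 1).

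Much of this stands as mitigation. It does not close the gap. The review depends on someone raising a concern, the extra ECG is optional, the intervening visits carry no ECG, and two sites could handle the same reading differently.

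A second reply is that a grade 2 row may have been lost when the PDF was read. The copy of Table 7 is visibly damaged: the sentence on recurrent grade 3 QTc has lost its instruction. Table 5 and Section 6.8.5 name only grades 3 and 4, which makes a lost row unlikely but does not exclude it.

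A reader might also infer that DLT counts, and so the MTD, are affected. The documents do not support that. Weekly ECGs in cycle 1 require a second ECG 5-9 days after a day 8 or day 15 reading, still inside the DLT window. For day 22, the confirming ECG falls outside cycle 1 only if it is done on day 29, and even then the event could be dated to its first reading. No frequency of QTc of 501 ms or more is given in the text as shown.

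**Conclusion.** The point holds as a gap in the safety instructions: on the visible text, one asymptomatic on-treatment QTc of 501 ms or more leads to no mandatory prompt repeat ECG or hold. The exposure is short in cycle 1 (5-9 days, or 3-8 days from day 22). It is long only when the reading falls at a visit followed by a two-cycle gap: 49-66 days from cycle 2 day 1. That is a worst-case wait under a strict reading, not a forecast of what sites would do.

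The conclusion assumes unextended cycles and that Table 7 has no grade 2 QTc row, which should be checked against the PDF. It does not mean that the protocol forbids action or lacks cardiology input, and it makes no claim about dose selection. This is a cheap improvement, worth making because it lets an existing safety rule work as intended.

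**What to change.** In Section 6.8.1:

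- Require any on-treatment QTc of 501 ms or more to be repeated at the same visit before further dosing, and apply the Table 7 grade 3 action if it is confirmed.
- State a follow-up ECG for an asymptomatic 481-500 ms, for example within 8 days, an interval that Section 6.8.3 and Table 7 already use. Put it in Section 6.8.1 or in a new Table 7 row, so that the pointer leads somewhere.

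Do not import the mandatory hold from Section 6.8.3 for 481-500 ms. In cycle 1 such holds could cost patients the minimum of 6 AR-42 and 21 pazopanib doses needed for DLT evaluability (Section 6.7.1), which is a debatable trade-off. No change to the DLT definition is needed.

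The cost is one extra ECG at an existing visit for each reading of 501 ms or more, possibly a brief dose delay, occasional follow-up ECGs for grade 2, and amendment wording. In cycle 1 the scheduled ECGs, 3-9 days apart, already meet most of the 8-day requirement.

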6.9 General Concomitant Medication and Supportive Care Guidelines

6.9.1 Nausea/Vomiting

Anti-emetics should be prescribed as clinically indicated.

6.9.2 Diarrhea

Diarrhea, a common side effect of pazopanib and AR-42, can be managed with loperamide. The recommended dose of loperamide is 4 mg at first onset, followed by 2 mg every 2 to 4 hours until diarrhea-free for 12 hours. Clinically significant diarrhea should be managed aggressively to prevent electrolyte abnormalities and dehydration. Anti-diarrheal prophylaxis should be considered in subsequent cycles.

6.9.3 Fluid and Electrolyte Replacement

- Patients who develop nausea, vomiting, diarrhea, mucositis, anorexia, or other toxicity that can contribute to fluid loss or inadequate fluid intake should be carefully monitored. Fluids should be administered, as indicated, to prevent and/or treat dehydration and to minimize the risk of postural hypotension and renal failure.
- To reduce the risk for prolongation of the QT interval, electrolyte levels (ie, potassium, magnesium, and calcium) should be checked according to the requirements on the study calendar (Table 19 and Table 20). Replacement of electrolytes, if needed, is at the investigator's discretion. Recheck serum potassium, magnesium, and calcium levels after replacement and consider chronic supplementation of potassium, magnesium, and/or calcium.

6.9.4 Palmar-plantar Erythrodysesthesia

PPE, also known as hand-foot skin reaction, has been reported in patients taking pazopanib. Biopsy specimens of patients with PPE secondary to tyrosine kinase inhibition show hyperkeratosis, keratinocyte necrosis, and dermal inflammation. In 240 patients with STS, about 11% of patients who received pazopanib experienced PPE compared to 1% taking placebo.

PPE, associated with pain and limitations in activities of daily living (ADL), may require treatment interruption and/or dose modification. Pazopanib dose modification instructions for PPE are provided in Table 9.

6.9.4.1 PPE Prevention

- Before initiating pazopanib treatment, check the condition of the patient's hands and feet. Suggest a manicure/pedicure, when indicated. Recommend use of a pumice stone for callus or rough spot removal. During pazopanib treatment, instruct patients to avoid pressure points and items that rub, pinch, or create friction.
- Instruct the patient to apply moisturizing lotions to their hands and feet twice each day throughout treatment.

6.9.4.2 PPE Treatment

Treatment may begin at the first clinical signs of PPE. At first occurrence, independent of grade, supportive measures should be promptly initiated.

- Instruct the patient to protect tender areas as follows:
 - Use socks/gloves to cover moisturizing creams
 - Wear well-padded footwear; use insole cushions or inserts.
 - Soak feet in tepid water and Epson salts.
- Creams may be used as follows:
 - Non-urea-based creams may be applied liberally.
 - Keratolytic creams (eg, urea-based creams, salicylic acid 6%) may be used sparingly and only to affected (hyperkeratotic) areas.
 - Alpha hydroxyl acids (AHA)-based creams may be applied liberally twice each day. Approximately 5% to 8% strength provides gentle chemical exfoliation.
 - Topical analgesics (eg, lidocaine 2%) may be used for pain control.
 - Topical corticosteroids (eg, clobetasol 0.05%) should be considered for patients with grade 2 or grade 3 PPE. Systemic steroids should be avoided.
- Use of Celecoxib

A meta-analysis of PPE prevention strategies concluded, with statistically significant results, that celecoxib was the most promising agent (26). Therefore, to reduce the severity of pazopanib-related PPE, celecoxib is recommended as follows:

- Celecoxib 200 mg once daily may begin at the first clinical signs or symptoms of grade 2 PPE.
- When PPE resolves, celecoxib 200 mg once daily throughout each treatment cycle, even in the absence of signs or symptoms of PPE, is recommended.

6.9.5 Hypertension

Hypertension, including hypertensive crisis, has been observed during pazopanib therapy. Hypertension should be managed aggressively to prevent complications. Management of hypertension is at the investigator's discretion.

- BP will be monitored weekly during the first 6 weeks of study treatment, at the beginning of every cycle beginning with cycle 3, and as clinically indicated throughout study treatment.
- Refer to Table 7 for grading definitions to be used for pazopanib dose modifications related to hypertension and for treatment instructions. CTCAE v4.0 will be used to grade hypertension for AE reporting purposes.

Note: Grade 3 hypertension will not be considered a DLT unless the patient is experiencing symptoms of hypertension and/or grade 3 hypertension persisted longer than 7 days. This guideline also applies to hypertension requiring an additional antihypertensive agent(s).

6.9.6 Anemia

Tranfusions, if necessary per the investigator, are permitted.

6.10 Prohibited/Discouraged Medications

- Cancer treatment, other than the treatment specified in the protocol, is not permitted.
- Non-prescription nutritional and dietary supplements are discouraged but not prohibited unless the supplement is known to interact with or modulate drug metabolism pathways, eg, St. John's wort. **Supplements known to have adverse effects on the liver are prohibited.** If nutritional and/or dietary supplements are used, the dose and schedule of the supplements should be documented.
- Hepatotoxicity is a known toxicity of pazopanib. Concomitant use of pazopanib and simvastatin increases the incidence of ALT elevations and should be avoided. Also, acetaminophen may confound interpretation of hepatotoxicity and should, therefore, be avoided when possible.
- Drugs and other substances that inhibit or induce cytochrome P450 3A enzymes.

Refer to Section 4.2.19 for additional information regarding prohibited or discouraged medications. If such medications have been used, the patient must have discontinued these agents \geq 1 week before starting/resuming pazopanib.

- Coadministration of pazopanib with strong inhibitors of CYP3A4 (eg, ketoconazole, ritonavir, clarithromycin) should be avoided.
- Coadministration of CYP3A4 inducers (eg, rifampin) may decrease plasma pazopanib concentrations and should be avoided.
- Grapefruit and grapefruit juice should be avoided.
- Concomitant treatment with strong inhibitors of P-gp or BCRP should be avoided due to risk of increased exposure to pazopanib.

• Concomitant use of pazopanib with drugs that raise gastric pH should be avoided. If such drugs are needed, short-acting antacids should be considered in place of proton pump inhibitors and H2-receptor antagonists. The antacid and pazopanib dosing should be separated by several hours to avoid a reduction in pazopanib exposure.

6.11 Study Pocket Card for Patients

A pocket card identifying the name of the study, the names of the study medications, and contact information including the study team and a 24-hour on-call study physician will be provided to each patient. The purpose of this card is to facilitate communication between the study team and the patient's health care providers not involved with the study. Patients will be encouraged to carry the card with them at all times and to show it to their health care providers so that potential interactions with the study medications can be identified before initiating new medications.

6.12 Elective Surgery During Study Participation

Both study medications should be held at least 2 weeks prior to scheduled surgery. Any plans for elective surgery should be discussed with the Sponsor-Investigator.

6.13 Follow-Up Period

Patients who discontinue treatment **for any reason other than consent withdrawal** remain on study in follow-up status for a 30-day evaluation period following the last dose of both study medications. During this 30-day post-treatment period, resolution or stabilization of ongoing treatment-related AEs and evolution of new treatment-related AEs will be reported. Additionally, if the patient has not had tumor progression, tumor response assessments performed during this 30-day follow-up period will also be reported.

Patients are off the study at the end of the 30-day follow-up period or when subsequent anticancer therapy begins, whichever occurs first. The primary reason(s) for a patient's discontinuation of study treatment and the patient's follow-up status will be recorded in the source documents and the CRFs.

